12.1 Visit 1 Baseline visit

Patients presenting with symptoms suggestive of pulmonary TB to one of the study clinics will be invited to be screened for inclusion in the study. Before any study-specific screening procedures will be performed, all patients will sign and date (or thumbprint) the latest version of the ICF. Illiterate participants will be encouraged to have a witness present.

After informed consent has been obtained, the patient will receive a study number. The ICF will be labelled with the study number. A primary health care nurse or dedicated researcher staff will administer a questionnaire (V1-D1) and ask the patient about their contact details and the contact details of a trusted proxy (locator form). In addition, 5 to 10% participants per site will be invited to answer a socio-economic questionnaire about income, cost of care seeking, productivity losses, diagnostics and treatment (V1-D1-SE). For these participants a face-to-face interview may be conducted.

Depending on the clinic, the patient will receive a diagnostic work-up according to the national algorithm (smear microscopy and/or off-site Xpert testing) or the study intervention (Truenat

Protocol short title: TB-CAPT CORE Truenat trial

Protocol Number: TB041-3/1 -MZ

Protocol Version: 4.0 - CONFIDENTIAL - Page 40 of 57

platform/TB assays on site). Further diagnostic investigations and TB treatment initiation will be as clinically indicated. All clinical care and further investigations will be provided within the governmental health care service. Patient details (including name, sex, age, and study-ID) will be documented in a study register, which will remain at the clinic. All patients will receive a study card with their details (including name, sex, age and study number and enrolment date) to take home with them. They will be asked to show the card if they present to the clinic again.

12.2 Visit 2: Day 7

All participants will be called by telephone 7 days after enrolment (between day 8 and day 21 after enrolment). Three attempts will be made to contact a participant by phone. If these attempts are unsuccessful the trusted proxy will be contacted to find out about the participant's whereabouts and arrange for a return call by the participants or a home visit. A home visit will be conducted for those participants who cannot be reached by phone.

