This is translated in terms of a mean difference (MD), comparing the intervention arm to the SOC arm.

 $H0: MD_{(int-SOC)} = 0 \text{ vs. } H1: MD_{(int-SOC)} \neq 0.$

Number of lost working days

The endpoint of interest is a continuous outcome.

H0: Mean lost working days in intervention arm is same as in the SOC arm vs.

H1: Mean lost working days in intervention arm is different from the SOC arm

This is translated in terms of a mean difference (MD), comparing the intervention arm to the SOC arm.

 $H0: MD_{(int-SOC)} = 0 \text{ vs. } H1: MD_{(int-SOC)} \neq 0.$

· Monthly earning

The endpoint is a continuous outcome.

H0: Mean monthly earning in intervention arm is same as in the SOC arm vs.

H1: Mean monthly earning in intervention arm is different from the SOC arm

QMS Form number: FM-06-02-	CONFIDENTIAL	Page 10 of 26
05/v2.0		-

FIND >>>	Statistical Analysis Plan		
Protocol number:	TB041-3/1-TAN / -MOZ		
Document version:	5.0	Document date:	11-JUL-2023

This is translated in terms of a mean difference (MD), comparing the intervention arm to the SOC arm.

 $H0: MD_{(int-SOC)} = 0 \text{ vs. } H1: MD_{(int-SOC)} \neq 0.$

Modeled cost and cost-effectiveness endpoints:

Unit costs of diagnosis and treatment, modified societal perspective

The endpoint will be calculated from measured costs from the patient and health system perspectives.

The primary outcome will be the sum of patient plus health system costs, expressed as unit costs (e.g., cost per test, cost per TB treatment), under the intervention and under the standard of care.

This outcome will not be subject to a formal statistical hypothesis test.

Incremental cost-effectiveness ratio, modified societal perspective

The endpoint will be calculated from cost and effectiveness outcomes, including both patient and health system perspectives.

The primary outcome will be the incremental cost per patient treated for TB, comparing the intervention to the standard of care.

This outcome will not be subject to a formal statistical hypothesis test, however the components that make up the outcome are.

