food costs incurred while in hospital, money spent buying any special foods). Indirect costs will be estimated as the opportunity cost of time spent seeking care (from the time of symptom onset to the time of treatment initiation), plus any lost productivity due to illness. Additional information from the scientific literature will be used to estimate costs that are not directly estimated (e.g., hospitalization costs, costs of TB treatment).

The total cost for each patient will be estimated as the sum of direct and indirect costs, and the mean cost will be taken as the sum of these total costs, divided by the number of patients.

Number of lost working days

We will use patient interviews to record the self-reported number of working days lost due to TB illness in both arms. This will be directly estimated; no additional statistical methods will be used. 95% confidence intervals will be calculated assuming a Poisson distribution.

Monthly earnings

To estimate loss in income, we will record the number of missed working days or missed working hours owing to TB illness, from the time of symptom onset to the time of treatment initiation. This number of days/hours will be multiplied by the average daily/hourly wage of employed laborers in each country to estimate the monthly earnings lost as a result of seeking care. If the patient does not have formal employment but works informally, e.g., as an agricultural worker, we will use their self-reported reduction in productivity (as a percentage of total productivity) over the course of the past year. This number will be multiplied by the average agricultural wage/earnings in each country and reported on a monthly basis. We will then calculate the mean monthly earnings lost as the sum of lost income (as described above), divided by the number of participants from which those data are obtained.

• Unit costs of diagnosis and treatment, modified societal perspective

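### SAP 2.2 tests mean monthly earning, but SAP 4.3 derives mean monthly earnings lost and pools two time windows and two scales in that one mean

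*SAP*

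**What the plan says.** SAP 2.2, among the direct cost and productivity endpoints, lists monthly earning as a continuous outcome. The null hypothesis is "Mean monthly earning in intervention arm is same as in the SOC arm", the alternative is two-sided, and the contrast is the mean difference, intervention minus standard of care.

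SAP 4.3, under monthly earnings, describes how the variable is built:

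- **Employed participants.** The count is of missed working days or "missed working hours owing to TB illness, from the time of symptom onset to the time of treatment initiation". It is multiplied by a country-average daily or hourly wage. The product is called monthly, but no division by a number of months is given.
- **Informal workers, such as agricultural workers.** Here "we will use their self-reported reduction in productivity (as a percentage of total productivity) over the course of the past year". That percentage is multiplied by a country-average agricultural wage or earnings figure and put on a monthly basis.
- **Summary.** "We will then calculate the mean monthly earnings lost as the sum of lost income", divided by the number of participants who supply such data.

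SAP 4.3 does not name the interview that feeds the variable. Protocol 10.1 lists loss of income at Visit 1, on the extended socio-economic form only. Protocol 9.11 has that subset answer an extended form at baseline and again at the last visit (V3-D60-SE), which Protocol 9.8 places at days 61 to 90. Protocol Table 1 names only the Visit 1 extended form as the source for the cost endpoint and has no row for earnings.

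**The concern.** The variable named in the hypothesis is not the variable the methods section produces, and the two have opposite favourable directions. An analyst who follows SAP 4.3 and reports under SAP 2.2 would present a difference whose sign the plan does not define.

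The derived variable is also not one quantity. The employed part is a total over an illness episode; the informal part is a monthly rate over a fixed past year. Their mean depends on the mix of employment types in each arm as well as on any loss of earnings. A past-year question also reaches back mostly or wholly before enrolment, when on-site testing could not yet have helped that participant.

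Effect of the assays on productivity is a stated secondary objective (Protocol 8.2), and this is one of the endpoints that the SAP tests for it. SAP 1.2 has the cost and productivity endpoints analysed throughout the study, so waiting for database lock will not by itself settle the definition.

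**Working it through.** The plan gives no sample size, standard deviation or effect size for monthly earnings, so there is no planned figure to reproduce. The check compares the two sections and works out the windows and scales.

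**1. Tested against derived variable.** Let a participant's potential monthly earning be E and the loss be L, so that the earning is Y = E − L. If E is the same in both arms, the mean difference in Y is minus the mean difference in L. An intervention that cuts the mean loss by d gives +d under SAP 2.2 and −d under SAP 4.3. Y cannot be recovered from SAP 4.3 either: losses are priced at a country wage, and the participant's own income, although asked about on the extended form, is not used.

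**2. Scale of the two components.** Assume D days of complete loss, all inside both windows, the same daily value w for both kinds of worker, and the informal percentage applied to a monthly wage of 365w/12.

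- Employed, as written: D × w.
- Informal, as written: (D/365) × (365w/12) = Dw/12.

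The same loss enters at scales that differ by a factor of 12. For D = 30 the contributions are 30w and 2.5w. If the employed total was meant to be divided by the length of the episode in months, m, it becomes Dw/m. That matches the informal figure only when m = 12.

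**3. Share of the past-year window after enrolment** (interview day/365).

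| Interview | After enrolment | Before enrolment |
|---|---|---|
| Visit 1 | 0% | 100% |
| Visit 3, day 61 | 61/365 = 16.7% | 83.3% |
| Visit 3, day 90 | 90/365 = 24.7% | 75.3% |

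Even if every day gained were otherwise a total loss, starting treatment 7 days earlier moves the annual percentage by at most 7/365 = 1.9 points, and 30 days earlier by at most 30/365 = 8.2 points.

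**4. End of the employed window.** The window closes at start of treatment. The planning prevalence of TB is 12% to 20%, so most of those enrolled would not be expected to have TB, and SAP 4.3 gives no end date for anyone never treated. If Visit 1 is the source, people already on treatment have been excluded, so the closing event has not yet occurred for those interviewed before they start. The employed component would then carry little information about arm as well.

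**The case against.** **The sign problem is a label.** The test is two-sided, and SAP 4.3 says plainly that it computes a loss. Correcting SAP 2.2 would settle this part, and the p-value is unaffected once one variable is chosen. That stands, but it does not resolve the pooling.

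**Reduced scale is not reduced power.** A reader might infer that the past-year question weakens the comparison 4- to 6-fold (365/90 = 4.1, 365/61 = 6.0). The documents do not support that. Past-year loss is pre-enrolment loss plus post-enrolment loss, so the arm difference in money lost is the post-enrolment difference, and dividing by 12 months rescales it. Precision suffers only through the variance of pre-enrolment loss and recall error, and the documents give neither. This objection stands for Visit 3. At Visit 1 there is no post-enrolment loss to rescale.

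**Scope.** A reader might conclude that the productivity objective as a whole can barely register an arm effect. That goes too far. The past-year rule covers informal workers only, their share is not given, and lost working days is a separate endpoint without that rule. Nor is the excess window pre-randomisation: clinics are randomised before patients are recruited, so the correct term is pre-enrolment.

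**Untreated participants.** The text counts time missed because of TB illness, so someone without TB could be scored zero or not applicable. That reading is possible, but the SAP does not state it. A reader might also put the number with an end date at 15 to 32, from planned success proportions of 0.12 × 0.89 × 0.98 × 0.90 = 0.0942 and 0.12 × 0.70 × 0.90 × 0.80 = 0.0605: 100 × 0.1547 = 15.5 for a subset of 200, and 210 × 0.1547 = 32.5 for 420. Those are confirmed starts within 7 days only. Later and clinically diagnosed starts also close the window, and the documents give no rate for them.

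**Some of these endpoints are descriptive.** SAP 4.3 says so in general terms. SAP 2.2 nevertheless gives monthly earning an explicit null and alternative, while it exempts unit costs and the cost-effectiveness ratio from testing.

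**The window is a choice of estimand.** This stands. Loss between onset and treatment is a legitimate cost quantity, so the remedy should not impose a single replacement window.

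**Conclusion.** The monthly-earnings endpoint is wrong as written and should be corrected before it is analysed. Two findings rest on the text alone: the tested and derived variables differ and have opposite favourable directions, and the derived mean combines an episode total with a monthly rate over a different window. The factor of 12 in scale rests on the literal reading and the equal-wage assumption stated above.

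For informal workers, 0% (Visit 1) or 17% to 25% (Visit 3) of the window lies after enrolment. That component therefore cannot show an effect arising after enrolment, or shows it on a much reduced scale. The consequence for the pooled mean cannot be quantified, because neither the share of informal workers nor any variance is given. No loss of power is demonstrated, and the point does not extend to lost working days or to the primary endpoint.

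**What to change.** - **SAP 2.2:** restate the hypothesis on mean monthly earnings lost, and say that a negative difference (intervention minus standard of care) favours the intervention.
- **SAP 4.3:** name the interview that supplies the data. Use one window and one unit, loss per month, for every sampled participant, formal or informal, treated or not. Enrolment to day 60 from V3-D60-SE is one option where the form supports it; the form itself is not in the documents. Report pre-enrolment loss separately.
- **If the form holds only a past-year question for informal workers:** report that component descriptively, and neither pool nor test it.

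The cost is mainly SAP wording, plus possibly one reworded recall question for participants not yet interviewed. The SAP is dated July 2023 and the protocol planned follow-up into Q4 2023, so few may benefit from new wording. Past-year answers already collected would become descriptive only. The onset-to-treatment loss used in the patient-cost work must be kept as a separate, separately named quantity.

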9.6.1 Primary endpoint

The primary endpoint is the estimate of the number and proportion of participants with microbiological confirmation starting TB treatment within 7 days of their first visit among enrolled participants.

Protocol Version: 4.0 - CONFIDENTIAL - Page 32 of 57

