2.1 Primary endpoint

The primary outcome of the study is the absolute number and point estimate (with 95% CIs) of the proportion of participants with TB microbiological confirmation starting TB treatment within 7 days of their first visit. We evaluate the probability of the patients in the intervention arm (with Truenat) for a favourable outcome of interest compared to patients in the SOC arm as a binary outcome of success or failure.

The hypotheses of interest are:

and,

 ${\it H0}:$ Number of successes in intervention arm is same as in the SOC arm.

H1: Number of successes in intervention arm is different from the SOC arm

H0: Proportion of success in intervention arm is same as in the SOC arm.

H1: Proportion of success in intervention arm is different from the SOC arm

This is translated in terms of odds ratio (OR) for odds of success in the intervention arm to be different from the odds of success in the SOC arm thus leading to the definition of the following hypothesis:

QMS Form number: FM-06-02-	CONFIDENTIAL	Page 6 of 26
05/v2.0		-

FIND >>>	Statistical Analysis Plan		
Protocol number:	TB041-3/1-TAN / -MOZ		
Document version:	5.0	Document date:	11-JUL-2023

 $H0: OR_{Intervention:SOC} = 1 \text{ vs. } H1: OR_{Intervention:SOC} \neq 1$

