H0: Number of pulmonary TB patients starting treatment in the intervention arm is same as in the SOC arm.

H1: Number of pulmonary TB patients starting treatment in the intervention arm is different from the SOC arm

And,

H0: Proportion of pulmonary TB patients starting treatment in the intervention arm is same as in the SOC arm.

H1

: Proportion of pulmonary TB patients starting treatment in the intervention arm is different from the SOC arm

This is translated in terms of odds ratio (OR) for the odds of TB treatment start in the intervention arm to be different from the SOC arm leading to the hypothesis:

$$H0: OR_{Intervention:SOC} = 1 \text{ vs. } H1: OR_{Intervention:SOC} \neq 1$$

Absolute number and point estimate with 95% Cis of the proportion of participants with signs and symptoms of pulmonary TB starting TB treatment without microbiological confirmation within 7 and 60 days from enrolment

 Absolute number and point estimate (with 95% CIs) of the proportion of enrolled participants with signs and symptoms of pulmonary TB starting TB treatment regardless of microbiological confirmation within 7 and 60 days from enrolment

The hypothesis from the previous point is repeated here at the specific time points instead of within the interval of 60 days.

QMS Form number: FM-06-02-	CONFIDENTIAL	Page 8 of 26
05/v2.0		-

FIND	Statistical Analysis Plan		
Protocol number:	TB041-3/1-TAN / -MOZ		
Document version:	5.0	Document date:	11-JUL-2023

• Estimate of time to TB treatment initiation for those with microbiological confirmation and for all participants (censored at 60 days) from enrolment

The endpoint of interest is a time-to-TB-treatment-initiation for those with microbiological confirmation and censored at 60 days from enrolment.

H0: Time to treatment intitiation in intervention arm is same as in the SOC arm vs.

H1: Time to treatment intitiation in intervention arm is different from the SOC arm

This is translated in terms of hazard ratio (HR) for the hazards of TB confirmation in the intervention arm is significantly different from the SOC arm or the instantaneous rate of TB treatment initiation after TB microbiological confirmation to be different in the two arms leading to the hypothesis:

 $H0: HR_{Intervention:SOC} = 1 \text{ vs. } H1: HR_{Intervention:SOC} \neq 1$

- Absolute number and point estimate (with 95% CIs) of the proportion of enrolled participants with ongoing treatment (on treatment) among:

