This quantity will be estimated as the incremental cost of the intervention (cost of intervention minus cost of standard of care), divided by the incremental effectiveness (i.e., incremental number of people diagnosed and treated in the intervention versus the standard of care). As above, a modified societal perspective will be used for both costs and effectiveness. The cost component of this equation will be estimated as described in the "unit costs" section above; the effectiveness component will be estimated as described for the primary outcome above. We will estimate uncertainty in this quantity using a simulation approach, where we draw independent simulations from the distribution of the primary outcome as inferred from the 95% confidence interval of the primary effectiveness outcome, as well as from the distribution of unit costs based on the empiric distribution of unit costs from our measurements above. We will report 95% uncertainty intervals as the outcomes falling within the smallest area covering 95% of the simulated costs and effectiveness values, plotted on a cost-effectiveness plane. We will perform these analyses separately by country.

BIA and ECEA of TB diagnostic tools.

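### The cost-effectiveness ratio is labelled per patient treated for TB, but its denominator counts only microbiologically confirmed patients who start within 7 days

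*SAP*

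**What the plan says.** SAP 2.2 (modelled cost and cost-effectiveness endpoints) defines the ratio: "The primary outcome will be the incremental cost per patient treated for TB, comparing the intervention to the standard of care". SAP 4.3 describes the denominator in similar terms, as the "incremental number of people diagnosed and treated in the intervention versus the standard of care". Neither sentence sets a time limit or requires microbiological confirmation.

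SAP 4.3 then says how that denominator is obtained: "the effectiveness component will be estimated as described for the primary outcome above". For uncertainty, "we draw independent simulations from the distribution of the primary outcome as inferred from the 95% confidence interval of the primary effectiveness outcome".

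The primary outcome in SAP 2.1 concerns "participants with TB microbiological confirmation starting TB treatment within 7 days of their first visit", analysed "as a binary outcome of success or failure". Protocol 9.6.1 puts it over everyone enrolled: "participants with microbiological confirmation starting TB treatment within 7 days of their first visit among enrolled participants".

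SAP 2.2 also lists a secondary endpoint that fits the ratio's label, participants "starting TB treatment regardless of microbiological confirmation within 7 and 60 days from enrolment".

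On the cost side, SAP 4.3 measures the opportunity cost of care-seeking from symptom onset to treatment initiation. It adds patient and health system costs into a per-patient cost of diagnosis and treatment. Nothing is cut at day 7.

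**The concern.** The label and the estimator describe different quantities. A confirmed participant who starts on day 15, or one who starts on clinical grounds at any time, has been treated for TB but is a failure in the denominator. The same participant's care-seeking costs can still enter the numerator.

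This matters because the omitted starts need not be balanced between arms. SAP 1.1 describes central Xpert testing as requiring sample transport, return of results and recall of the patient, and SAP 4.3 describes standard of care as mainly off-site testing. More late or clinical starts under control are therefore plausible. In that case the incremental number treated is overstated and the cost per additional patient treated looks too low.

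Protocol section 7 says the findings are meant to inform decisions on use and scale-up. Readers of a cost per patient treated would take the label at face value.

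**Working it through.** **1. Who counts as treated.**

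| Participant | Treated for TB (SAP 2.2 label) | Success in the denominator (SAP 4.3) |
|---|---|---|
| Confirmed, starts by day 7 | yes | yes |
| Confirmed, starts days 8 to 60 | yes | no |
| Clinically diagnosed, starts by day 7 | yes | no |
| Clinically diagnosed, starts days 8 to 60 | yes | no |

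The middle column follows the SAP's own usage: a diagnosis-related endpoint in SAP 2.2 splits patients treated for TB into those diagnosed microbiologically and those diagnosed clinically.

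**2. Whether only the model is borrowed.** SAP 4.3 could mean that the effect on all starts is estimated with the same type of model. The simulation sentence rules this out, because it draws from the confidence interval of the primary effectiveness outcome itself. SAP 2.2 also uses the term primary outcome for the ratio, but the ratio cannot supply its own effectiveness component.

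**3. The planning difference.** The documents state no ratio and no denominator for it, so there is nothing to reproduce directly. The nearest figures are the success proportions behind the sample size (Protocol 13.8, SAP 8; selected scenario), from p = prevalence × sensitivity × (1 − diagnostic LTFU) × (1 − pre-treatment LTFU):

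- Intervention: 0.12 × 0.89 × 0.98 × 0.90 = 0.0942
- Control: 0.12 × 0.70 × 0.90 × 0.80 = 0.0605
- Difference: 0.0337, or 3.4 per 100 enrolled

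Put into the documents' cluster-pair formula with cluster size 150 and coefficient of variation 0.25, these give A + 11.95. With the protocol's A = 1 that is 12.95, rounded up to the stated 13 pairs, so the inputs are read correctly. (The SAP states A = 2, which would give 14; that is a separate matter.)

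**4. Illustration.** Assume that the incremental cost is fixed and that late or clinical starts close a share s of the difference by day 60. The all-starts difference is 3.37 × (1 − s) per 100, and the ratio is multiplied by 1/(1 − s).

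| Share closed (assumed) | Difference per 100 | Ratio multiplied by |
|---|---|---|
| 0% | 3.4 | 1.0 |
| 25% | 2.5 | 1.3 |
| 50% | 1.7 | 2.0 |

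One way to get s = 25% is for a quarter of the TB patients not started by day 7 to start later in each arm. Each arm's proportion becomes p + 0.25 × (0.12 − p), so the difference shrinks to 0.75 × 0.0337 = 0.0253.

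**5. Direction.** Suppose instead that only the intervention arm has such starts, at the same 25%. Its proportion becomes 0.0942 + 0.25 × (0.12 − 0.0942) = 0.1006 and the difference 0.1006 − 0.0605 = 0.0402, using unrounded values. The ratio is then multiplied by 0.0337/0.0402 = 0.84, so the planned version would look too unfavourable.

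**The case against.** The strongest reply is that the SAP is open about its source, and that a denominator tied to confirmed TB matches the primary objective. Counting every start would also credit empirical treatment of people who may not have TB. The ratio has no formal hypothesis test, is not among the endpoints in Protocol 9.6.2, and leaves the primary conclusion untouched. The 60-day and any-start results are reported separately. All of this stands: the 7-day confirmed denominator is a legitimate choice. It does not rescue the label, which promises something else.

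A reader might infer three stronger claims that the documents do not support.

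- *The ratio is biased in favour of the intervention.* No late or clinical starts are given by arm. Control care also includes smear microscopy, which Protocol 5.4 calls the main tool in Mozambique, so delay in that arm is not uniform. The direction is plausible, not established.
- *The distortion could be fourfold, if 75% of the difference closes.* The planning formula has no 7-day term; it models missed cases and losses. Sensitivity alone accounts for 0.12 × 0.19 × 0.72 = 0.0164 to 0.12 × 0.19 × 0.882 = 0.0201 of the 0.0337, or 49% to 60%. Late starts among patients already detected cannot recover that part; clinical diagnosis or repeat testing would have to. The multipliers also need a fixed numerator, and the SAP does not say whether treatment cost attaches to all starters or only to those counted as effects.
- *The denominator cannot be computed because the primary model gives an odds ratio.* SAP 2.1 plans absolute numbers and proportions with confidence intervals, and SAP 4.2 adds a Poisson count model. An increment can be derived, although SAP 4.3 should name the scale.

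**Conclusion.** The mismatch holds on the text alone. As written, the plan would report a cost per additional microbiologically confirmed patient started within 7 days under the name of a cost per patient treated for TB. Effects stop at day 7 and require confirmation; the patient costs set against them do neither.

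Its size and direction are not known. The factors of 1.3 and 2.0 are illustrations. They rest on the planning proportions, a fixed incremental cost, and an assumed closure of 25% or 50% of the difference. The point concerns a secondary economic endpoint and should be corrected before analysis; it does not affect the trial's primary inference.

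**What to change.** In SAP 4.3, estimate the effectiveness component as the between-arm difference in the proportion starting TB treatment within 60 days, regardless of microbiological confirmation. Draw the simulations from that difference's confidence interval, by country, since SAP 4.3 runs this analysis separately by country. Keep the 7-day confirmed version as a sensitivity analysis, labelled as cost per additional microbiologically confirmed patient started within 7 days. State whether treatment cost attaches to every starter, so that numerator and denominator cover the same people.

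If the sponsor prefers the 7-day confirmed denominator, use that label for the ratio in SAP 2.2 and 4.3.

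Either route is a wording change. No new data are needed: the 60-day any-start endpoint is already planned, and treatment start dates are recorded in the study TB outcome worksheet (Protocol 9.8). The price of the first route is that the ratio may look less favourable and that its count includes people treated without confirmation.
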